### **6.6.2. Subject Replacement**

There will be no subject replacement in the LTS Study.

### **6.6.3. Study Discontinuation**

The Sponsor reserves the right to discontinue the study at any time for any reason.

Periodic reviews of accumulating data by the IDMC may lead to the committee's recommendation of pausing dosing or terminating the Study. In the event of premature Study termination, best efforts to guarantee appropriate safety follow-up of subjects who have already been enrolled will be made and IRB/IEC/REBs and the Regulatory Authorities will be informed.

### **6.7. Pregnancy**

If a female subject or the partner of a male subject becomes pregnant during the Study or within 7 days of the subject's last dose of Study drug, the Sponsor clinical Study director (or designee) must be notified immediately. If the female subject is still on Study drug treatment, the Study drug must be discontinued immediately. Follow-up information regarding the outcome of the pregnancy and any postnatal sequelae in the infant will be required.

All pregnancies whether by the subject participating in the Study or the female partner of the male subject in the Study should be reported within 24 hours of awareness using the Pregnancy Notification Form.

## 7. ADVERSE EVENTS

### 7.1. Definitions

The definitions below are based on International Conference on Harmonization (ICH) guideline E2A, “Clinical Safety Data Management: Definitions and Standards for Expedited Reporting”.

#### 7.1.1. Adverse Events (AE)

An AE on Protocol 0164 (LTS) is any AE that occurs after the first dose of study drug. An AE prior to the first dose of study drug on Protocol 0164 (LTS) will be documented in the 0157 Study and if continuing at the time of consent to Protocol 0164 (LTS), the AE will be documented in the Protocol 0164 (LTS) database as an ongoing event.

An AE is any untoward medical occurrence in a patient or clinical trial subject administered a pharmaceutical product that does not necessarily have to have a causal relationship with this treatment. An AE can therefore be any unfavorable and unintended sign (including an abnormal laboratory finding), symptom, or disease temporally associated with the use of a medicinal product, whether or not related to the medicinal product.

- AEs may be new events
- Preexisting events that increase in frequency, severity or change in nature or seriousness during or as a consequence of participation in clinical studies.
- Pre- or post-treatment complications that occur as a result of a protocol-mandated procedure [REDACTED]
- AEs may be clinically significant changes from baseline in physical examination, laboratory tests, or other diagnostic investigation (e.g., laboratory results, x-ray findings).
- AEs may result from an overdose of the Study drug.

Whenever possible, the diagnosis (rather than a series of terms related to a diagnosis) should be recorded as the AE term.

An AE does not include the following:

- Medical or surgical procedures (such as surgery, [REDACTED], tooth extraction, or transfusion); the condition that leads to the procedure is an adverse event
- Preexisting diseases or conditions present or detected before signing an informed consent form that do not worsen
- Situations where an untoward medical occurrence has not occurred (such as hospitalization for elective surgery or social and/or convenience admissions)
- Overdose of either Study drug or concomitant medication without any signs or symptoms, unless the subject is hospitalized for observation

Any medical condition or clinically significant laboratory abnormality with an onset date prior to the time the subject signed the informed consent form is considered to be preexisting and should be documented in the medical history CRF.

Pregnancy is not an AE; however, if a female subject becomes pregnant during the conduct of the Study, the sponsor, will be notified according to the procedures for SAE reporting as outlined in Section 7.4.3. Follow-up information regarding the outcome of the pregnancy and any fetal or neonatal sequelae will be obtained and documented.

### **7.1.2. Serious Adverse Event (SAE)**

A serious adverse event (SAE) is defined as any untoward medical occurrence occurring at any dose that results in any of the following outcomes:

- Death
- Life-threatening situation. “Life-threatening” refers to a situation in which the patient was at risk of death at the time of the event; it does not refer to an event which might have caused death if it were more severe.
- Inpatient hospitalization or prolongation of existing hospitalization

Note: “Inpatient hospitalization” means the subject has been formally admitted to a hospital for medical reasons, for any length of time. This may or may not be overnight. It does not include presentation and care within an emergency department. A scheduled hospitalization for a pre-existing condition that has not worsened during participation in the Study does not meet this criterion. Pre-planned hospitalizations for an elective medical/surgical procedure, scheduled treatments, or routine check-ups do not meet this criterion. Complications that occur during hospitalizations are AEs. If a complication prolongs hospitalization, it is an SAE.

- Congenital anomaly/birth defect in the offspring of a subject who received Study drug
- Disability. A persistent or significant incapacity or substantial disruption to the ability to conduct normal life functions.
- Important medical events that may not result in death, be immediately life-threatening, or require hospitalization, may be considered an SAE when, based upon appropriate medical judgment, they may jeopardize the subject and may require medical or surgical intervention to prevent one of the outcomes listed in this definition. Examples of such events are as follows:
  - Intensive treatment in an emergency room or at home for allergic bronchospasm
  - Blood dyscrasias or convulsions that do not result in hospitalization
  - Development of drug dependency or drug abuse

### **7.1.3. Additional Considerations for Serious Adverse Events**

- Death is an outcome of an adverse event and not an adverse event in itself. Deaths of unknown cause for which the investigator cannot identify a cause of death will be captured as death of unknown cause or death not otherwise specified.

- All deaths, regardless of cause, must be reported for subjects if the death occurs while the subject is participating in the Study.
- “Occurring at any dose” does not imply that the subject is receiving Study drug at the time of the event; dosing may have been given as treatment cycles or interrupted temporarily before the onset of the SAE, but may have contributed to the event.

#### **7.1.4. Adverse Events of Special Interest (AESI)**

At each Study visit, the Investigator (or designee) will specifically query for any adverse events of special interest (AESI). The following events are considered AESIs for this Study:

- Suspected or confirmed intestinal perforation
- Complicated herpes zoster (multi-dermatomal, disseminated, or with ophthalmic or CNS involvement)
- Malignancy excluding non-melanoma skin cancer
- Non-melanoma skin cancer
- Serious infection (e.g., that requires hospitalization or intravenous antimicrobials)
- Opportunistic infections
- Thromboembolic disease (e.g., deep vein thrombosis (DVT), pulmonary embolism)
- Clinical laboratory abnormalities of concern (Refer to Section 7.2)
- Major cardiovascular event (e.g., myocardial infarction or cerebrovascular accident)

All AESIs, except for non-melanoma skin cancers and mono-dermatomal herpes zoster, must be reported to TBPH Clinical Safety and Pharmacovigilance within 24 hours of the time the Investigator or his/her designee becomes aware of an AESI (Refer to Section 7.1.4). Except for non-melanoma skin cancer that has been fully resected, mono-dermatomal herpes zoster, and certain laboratory abnormalities that are deemed by the investigator to not place subjects at immediate safety risk, all of these AESIs should lead to discontinuation of the study drug. For each of these AESI, an additional targeted questionnaire needs to be completed to assess for risk factors. For thromboembolic events in particular, the subject should undergo evaluation for hypercoagulable state (e.g., with clinically relevant investigations, such as referral to a specialist and/or blood testing for a predisposition to a hypercoagulable state) and repeat imaging to assess resolution of the finding.

Besides these AESI, for other AEs, study drug may be interrupted and resumed as deemed medically appropriate by the investigator (e.g., during an infection that requires oral antimicrobial treatment).

## 7.2. Clinical Laboratory Abnormalities and Other Abnormal Assessments as Adverse Events or Serious Adverse Events

Abnormal laboratory findings (such as clinical chemistry, hematology, or urinalysis) or other abnormal assessments (such as electrocardiograms [ECGs], X-rays, or vital signs) that are associated with signs and/or symptoms or are considered clinically significant in the judgment of the investigator must be recorded as AEs or SAEs if they meet the definition of an adverse event (or serious adverse event), as described in Section 7.1.1 (Adverse Event) and Section 7.1.2 (Serious Adverse Event).

Clinical laboratory abnormalities of concern may include, but are not limited to, the following where the investigator must recheck within 2-7 days, except for AST or ALT > 3x ULN where these need to be rechecked within 48-72 hours, as deemed appropriate by the investigator:

- clinically significant reduction in neutrophils or leukocytes or lymphocytes that may place subjects at higher risk for infection such as:
  - moderate or severe neutropenia (e.g., absolute neutrophil count of < 1.0 x 10^9/L)
  - moderate or severe leukopenia (e.g., white blood cell count of < 2.0 x 10^9/L)
  - moderate or severe lymphocytopenia (e.g., absolute lymphocyte count of < 0.5 x 10^9/L)
- abnormal hepatic panel (AST or ALT > 3x ULN)
- an excessive decrease in creatinine clearance [e.g., a reduction by ≥ 50% from baseline (baseline for this purpose is defined as creatinine clearance calculated for Day 1, predose activities)]

Depending on the subject's baseline and individual scenario, the investigator should report as an AESI and stop study drug treatment if any of the below is seen:

- moderate or severe neutropenia (e.g., absolute neutrophil count of < 1.0 x 10^9/L) on two sequential laboratory reports
- moderate or severe leukopenia (e.g., white blood cell count of < 2.0 x 10^9/L) on two sequential laboratory reports
- moderate or severe lymphocytopenia (e.g., absolute lymphocyte count of < 0.5 x 10^9/L) on two sequential laboratory reports
- a reduction by ≥ 50% from baseline in creatinine clearance on two sequential laboratory reports
- ALT or AST > 8x ULN on a single laboratory report. Note: See [Appendix 6](#) for an algorithm of evaluating and managing subjects with ALT or AST > 3x ULN.
- Abnormal AST or ALT > 3x ULN on two sequential laboratory visits with bilirubin > 2x ULN on at least one of the two laboratory reports, or international normalized ratio (INR) > 1.5 on at least one of the two reports (INR will be checked locally)
- AST or ALT > 5x ULN on two sequential laboratory reports, least 2 weeks apart

- AST or ALT > 3x ULN associated with signs or symptoms suggestive of acute liver injury.

If there are any AE questions, the investigator is encouraged to contact the Sponsor to discuss.

Merely repeating an abnormal test does not constitute an adverse event. Any abnormal test result that is determined to be an error does not require reporting as an adverse event.

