**7.4.3. SAE and AESI Reporting Timeline**

SAEs and AESIs will be reported to Clinical Safety and Pharmacovigilance within 24 hours of the time the Investigator or his/her designee becomes aware that a SAE or AESI has occurred, whether or not the event is considered to be related to Study drug. If the initial SAE is reported by telephone, a written report signed by the Investigator must be submitted within 24 hours.

The SAE/AESI Report Form must be completed in accordance with the SAE/AESI Report Form Completion Guidelines. If all information on the SAE/AESI Report Form is not available at the time of the initial report, follow-up SAE/AESI reports will be completed and submitted.

To report an SAE or AESI, complete and fax or email the SAE/AESI Report Form to the following:

Theravance Biopharma Clinical Safety and Pharmacovigilance

[REDACTED]

For medical questions regarding an SAE, contact the Sponsor medical monitor by telephone as follows:

Sponsor Medical Monitor Contact Information:

[REDACTED]

For fatal or life-threatening events, also fax copies of hospital case reports, autopsy reports, and other documents when requested. Additional information may be requested from the investigator to ensure the timely completion of accurate safety reports.

An SAE may qualify for reporting to regulatory authorities if the SAE is possibly attributable to the Study drug and is unexpected/unlisted based on the current TD-1473 Investigator's Brochure. In this case, all investigators will receive notification of the event. The investigator is responsible for notifying the Institutional Review Board or Ethics Committee and documenting the notification, as required by local regulatory authorities and in accordance with the local institutional policy.

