3.4.2.1. Adverse Events of Special Interest

An AE of special interest (AESI) is one of scientific and medical interest specific to understanding the investigational product and may require close monitoring and rapid communication by the investigator to the sponsor. The following are the AESI's defined for the study:

- Suspected or Confirmed Intestinal Perforation
- Complicated Herpes Zoster (multi-dermatomal, disseminated, or with ophthalmic or CNS involvement)
- Malignancy excluding non-melanoma skin cancer
- Non-melanoma skin cancer
- Serious Infection (e.g., that requires hospitalization or intravenous antimicrobials)
- Opportunistic Infections
- Thromboembolic disease (e.g. deep vein thrombosis, pulmonary embolism)
- Clinical Laboratory Abnormalities of Concern
- Major Cardiovascular Event (e.g. myocardial infarction or cerebrovascular accident)

The incidence of AESI's will be summarized overall and by AESI category and preferred term.

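### Protocol 7.2 can be read two ways on when a laboratory abnormality is an AESI, and SAP 3.4.2.1 tabulates the category without saying which applies

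*Protocol*

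**What the plan says.** Protocol 7.1.4 names nine AESI categories. The laboratory entry reads "Clinical laboratory abnormalities of concern (Refer to Section 7.2" and carries no threshold of its own. Apart from two exceptions that are not laboratory findings, AESIs "must be reported to TBPH Clinical Safety and Pharmacovigilance within 24 hours", and Protocol 7.4.3 repeats that clock. AESIs should normally lead to stopping study drug, but 7.1.4 exempts, among others, "certain laboratory abnormalities that are deemed by the investigator to not place subjects at immediate safety risk".

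Protocol 7.2 then gives two lists.

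- **First list.** It opens: "Clinical laboratory abnormalities of concern may include, but are not limited to, the following where the investigator must recheck within 2-7 days". The entries are neutrophils below 1.0, leukocytes below 2.0 and lymphocytes below 0.5 (x 10^9/L), AST or ALT above 3x ULN (recheck in 48-72 hours), and a creatinine-clearance fall of at least 50% from baseline.
- **Second list.** Subject to the patient's baseline and circumstances, "the investigator should report as an AESI and stop study drug treatment if any of the below is seen". The three cytopenias and the creatinine-clearance fall recur with an added condition, as in "from baseline in creatinine clearance on two sequential laboratory reports". For AST/ALT the patterns are: above 8x ULN once; above 3x on two sequential occasions with bilirubin above 2x ULN or INR above 1.5 on at least one; above 5x on two sequential reports at least 2 weeks apart; or above 3x with signs or symptoms of acute liver injury.

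Protocol 8.6.1.1 tabulates the category by name and points back to 7.2. SAP 3.4.2.1 also names it and says that AESI incidence "will be summarized overall and by AESI category and preferred term". The SAP gives no threshold, no confirmation rule and no reference to either list.

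**The concern.** The term that 7.1.4 makes an AESI is the term that heads the recheck list, yet the explicit instruction to report an AESI comes with the second list. A site that reports a qualifying value at once can point to the text, and so can a site that waits for the second report. The laboratory row of the AESI table may therefore contain some unconfirmed values and some confirmed ones, with nothing in the SAP to separate them.

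Safety is the primary objective, SAP 1 excludes the efficacy analyses, and the AESI table is one of the named safety outputs. A reader of the report would want to know what that row counts. The 24-hour report would also start from a different result under each reading, but that can no longer be changed here: SAP 1 states that all last doses occurred by 09SEP2021.

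**Working it through.** The plan gives no figure to reproduce. The check sets the texts side by side.

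**1. Does another section settle the rule?** Protocol 6.6.1 summarises the laboratory criteria of 7.2 as two sequential occurrences, but as grounds for stopping drug. It does not say when to report. The exemption in 7.1.4 for abnormalities judged to carry no immediate risk allows laboratory AESIs that do not stop drug, which suggests a class wider than the stopping list. The second list joins reporting and stopping in one instruction, which suggests the opposite. Neither section decides it.

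**2. Can either count be read from other planned tables?** The relevant rules are:

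- SAP 3.4.3.1 counts subjects by timepoint for neutrophils, leukocytes and lymphocytes only, on single values.
- SAP 3.1 keeps unscheduled results out of summaries and derived parameters unless noted otherwise.
- SAP 3.1.4 selects the latest laboratory result at a visit.
- Protocol 8.6.3 planned a by-visit summary of abnormalities of concern. SAP Appendix 1 records only the dropped efficacy analyses, so the absence of creatinine-clearance and AST/ALT criteria is not explained.

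Applied to example subjects (values invented for illustration):

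| Subject | First list, any report | Second list | SAP 3.4.3.1 |
|---|---|---|---|
| Neutrophils 0.9 at Week 12, recheck 1.3 four days later | Yes | No | Counted if the recheck is unscheduled; not counted if it is entered under Week 12 |
| Neutrophils 0.9, recheck 0.8 | Yes | Yes | Counted as a single value; confirmation not shown |
| Creatinine clearance down 55%, recheck down 30% | Yes | No | No criterion |
| ALT above 3x but not above 5x ULN; bilirubin and INR normal, no symptoms | Yes | No | No criterion |

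Neither the any-report count nor the confirmed count can be relied on from the planned tables.

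**3. How far apart could the counts be?** For the cytopenia and creatinine-clearance criteria, let N subjects have at least one qualifying value and let a share p be confirmed on the next report. The any-report count is N, the two-report count is p x N, and the ratio is 1/p. The documents do not give p. Assuming 0.3, 0.5 and 0.7:

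- p = 0.3: 1/0.3 = 3.3
- p = 0.5: 1/0.5 = 2.0
- p = 0.7: 1/0.7 = 1.4

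If a share s of these subjects is at sites that report every first qualifying value, and the other sites wait for confirmation, the site-reported count is N x (s + (1 - s) x p). With an assumed N = 10 and p = 0.5 it runs from 10 x 0.5 = 5 (s = 0) to 10 (s = 1). This shows only the form of the effect. Real site reports also depend on investigator judgement.

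**The case against.** The best reconciling reading is that the first list only triggers a recheck and the second list alone defines the laboratory AESI. Section 7.1.4 defers to 7.2, and the second list is the only place in 7.2 that says to report an AESI. Section 6.6.1 uses the two-occurrence wording and then turns to AESIs unrelated to laboratory results. If one value were already an AESI, stopping drug would be the default at that value, leaving the two-report stopping rule little to do. This is a reasonable reading and may be the intended one. It does not remove the ambiguity, because 7.1.4 attaches AESI status to the very term that heads the first list, and no sentence limits it to the second.

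A reader might infer more than the documents support:

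- **That 7.1.4 makes any first qualifying value an AESI.** It does not say so; it refers to 7.2. The first list is also open-ended and hedged by clinical significance and investigator judgement, so one low neutrophil count is not automatically an AESI.
- **That the row cannot be interpreted by dose group.** The variation would be between sites, and dose is at least partially blinded (Protocol 3.3.2 and 3.3.3). Nothing suggests that a site would apply a different rule by dose.
- **That Protocol 7.2 should be rewritten to the first-value reading.** The text gives no ground for preferring it, and no edit can act now that dosing has ended.

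It is also fair to say that abnormal values are listed, that SAP 3.4.3.1 gives single-value counts for the three cytopenias, and that the table specifications and AESI form guidelines are separate documents, not seen here, which might state a rule.

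**Conclusion.** The point holds as an ambiguity inside Protocol 7.2 that the SAP carries into a reported count. It concerns all the laboratory criteria printed in 7.2, AST/ALT included. The consequence is an AESI row whose definition may differ between sites, with no planned table from which either definition can be reliably recovered.

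The size is unknown. The ratios of 1.4 to 3.3 rest on assumed confirmation shares and apply to counts derived from laboratory records, not to what sites actually reported. The table is descriptive, no inferential tests are planned, and safety monitoring as a whole is not impaired. This is a worthwhile, inexpensive improvement to the analysis plan.

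**What to change.** In SAP 3.4.2.1, state that the laboratory category is derived from all post-baseline laboratory records, scheduled and unscheduled, to last dose + 28 days, as an exception to SAP 3.1 and 3.1.4. That window matches the treatment-emergent definition in SAP 3.4.2. Show by treatment and overall the number of subjects:

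- (a) meeting a threshold in the first list of Protocol 7.2 on any report;
- (b) meeting a criterion in the second list, including the AST/ALT patterns as far as the collected data allow (INR is checked locally, and signs and symptoms are not laboratory data);
- (c) reported by the site as an AESI.

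Row (c) keeps the investigators' judgement visible, and rows (a) and (b) show what each list would count. Protocol 7.2 is left as it is.

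The cost is one additional derived variable and a few table rows. Creatinine clearance over time follows from the Appendix 2 formula, using serum creatinine from the chemistry panel with age, sex and height. It must be programmed, since SAP 3.2.3 does not list it even at baseline. No new data collection is needed.

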### **7.3. Assessment of Adverse Events**

All AEs will be assessed by the investigator and recorded in the case report form, including the dates of onset and resolution, severity, relationship to Study drug, outcome, and action taken with Study drug.

#### **7.3.1. Severity**

The term “severe” is often used to describe the intensity (severity) of a specific event (as in mild, moderate, or severe myocardial infarction); the event itself, however, may be of relatively minor medical significance (such as severe nausea). This is not the same as “serious,” which is based on patient/event outcome or action criteria usually associated with events that pose a threat to a subject’s life or functioning. The severity of AEs will be assessed according to the following definitions:

- **Mild:** the AE is noticeable to the patient and/or the Investigator, but does not interfere with routine activity.
- **Moderate:** the AE interferes with routine activity, but responds to symptomatic therapy or rest.
- **Severe:** the AE significantly limits the patient’s ability to perform routine activities despite symptomatic therapy.

